4 RESEARCH DESIGN

4.1 Study type

This is a national, cross-sectional, non-comparative, sample-based cost analysis survey.

Insofar as this study does not study the pathology itself, nor intervene in its management, it corresponds to research not involving the human person.

4.2 Assessment criteria

4.2.1 Main criterion

Average annualized cost per patient/family.

Table 2 below shows the typology of all the costs considered in this study.

Table 2: typology of all study costs.

		Postes de coûts recueillis dans le cadre de l'étude 'CouDuMyo'
Coûts directs	Coûts médicaux non remboursables	
 ▪ Médicaments en vente libre ▪ Autres produits de santé en vente libre (ex : petits dispositifs médicaux, compléments nutritionnels oraux...) ▪ Equipements techniques de compensation du handicap ▪ Consultations de professionnels paramédicaux non pris en charge par l'Assurance Maladie (ex : ergothérapeute ou psychologue en ville...)
	Coûts liés à la sphère médico-sociale	
 ▪ Auxiliaire de vie, éducateurs spécialisés, assistants sociaux, accompagnement à la scolarité ▪ Hébergement en établissement médico-social ▪ Consultations dans des services médico-sociaux
	Coûts non-médicaux	
 ▪ Adaptation du domicile, adaptation du véhicule ▪ Transports non médicaux ▪ Aide informelle pour les soins (aidant familial, bénévole, autre) ▪ Aide informelle pour les activités quotidiennes ▪ Recours à une aide hors secteur sanitaire pour les actes de la vie quotidienne (ménagère, auxiliaire de vie, etc.)
Coûts indirects	Coûts indirects pour le patient	
 ▪ Pertes de productivité (adulte) ▪ Perte de jours d'école (enfant)
	Coûts indirects pour les aidants	
Pertes de temps dédié :
 
 ▪ à une activité professionnelle (aidant travaillant), ▪ ou de loisir (aidant non travaillant), 
hors temps consacré aux soins².

Aides financières	Coûts liés aux allocations/aides financières	Dispositifs permettant de financer (hors budget de l'Assurance Maladie dans le cadre de l'ALD) tout ou partie des coûts identifiés (ex : allocation compensatrice pour personne tierce (ACTP), allocation adultes handicapés (AAH), allocation d'éducation de l'enfant handicapé (AEEH), prestations de compensation du handicap (PCH)...)

4.2.2 Secondary criteria

- Average annualized cost by type of cost and by patient/family ;
- Average annualized cost per patient/family for each stage of disease severity;
- Cost drivers identified.

² Pour ne pas comptabiliser double avec le coût des soins médicaux

5 ELIGIBILITY CRITERIA

5.1 Inclusion criteria

- Patients of any age with DMD diagnosed more than 6 months ago;
- Patients included in the BNDMR (ORPHA code: 98896), who do not object to the collection of their data (see BNDMR 'Agreement to be contacted for a protocol') and who are alive at the time they are asked to participate in the study.

Identified patients are those present in the BNDMR with an up-to-date address at their follow-up center.

5.2 Non inclusion criteria

- Patient participating in an interventional clinical study with modification of usual management (see BNDMR 'Patient participating in a protocol');
- Patient and/or primary caregiver objecting to the use of his/her data;
- Patient and/or primary caregiver whose understanding of the French language does not allow them to complete the questionnaire.

5.3 Patients identification in BNDMR

The CO BNDMR will provide the URC ECO with a secure file listing eligible patients identified by a specific identifier (ID_étude), as well as the variables of interest for sampling and the rare disease site considered.

The patient identification period runs from the start date of inclusions in the BNDMR (2017) to January 1, 2023.

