RATIO BENEFIT/RISK	This is a descriptive study, the aim of which is to analyze the costs borne by patients and their caregivers, as well as the costs associated with informal help, in the context of DMD management in France. No individual benefit is expected from participation in this study, which will contribute to improving knowledge of the various expenses associated with the disease. The only constraint for participants will be to answer a questionnaire. Overall, the benefit/risk balance for the privacy of patients and families is therefore acceptable.
SUBJECTS NUMBER	The sample size for 15% accuracy is 171 patient/caregiver pairs according to the recommendations of Johnston et al. 2019.
STUDY DURATION	Inclusion period: 6 months (01/2023 - 06/2023) Duration of participation for each subject: completion of questionnaire (30 minutes max) Total study duration: 6 months (01/2023 - 06/2023)
RESEARCH SITES	All French centers accredited by the DGOS and providing the usual care for DMD patients, and contributing to their registration in the BNDMR.
EXPECTED BENEFITS	
 - For patients and their carers: find out what patients and carers consume in connection with the disease, identify the most significant expenditure items, contribute to the development of the HAS ALD guides. - For HAS and the Comité Economique des Produits de Santé (CEPS): identify and quantify expenses associated with the disease in the absence of specific treatment. 
Knowledge of disease-related consumption (excluding direct medical costs) as a function of patient characteristics complements the EPARDYS study's collection of direct medical costs. It will thus provide a complete picture of Duchenne-related expenses borne by patients and caregivers in France.

LIST of ABBREVIATIONS

ALD	Affection Longue Durée
AP-HP	Assistance Publique Hôpitaux de Paris
BNDMR	Banque Nationale de Données Maladies Rares
CEPS	Comité Economique des Produits de la Santé
DGOS	Direction Générale de l'Offre de Soins
DMD	Dystrophie Musculaire de Duchenne
DPO	Data Privacy Officer - Délégué à la protection des données
DRCI	Direction de la Recherche Clinique et de l'Innovation
DSI	Direction des systèmes d'information
DSN	Direction des Services Numériques
HAS	Haute Autorité de Santé
MDPH	Maison Départementale des Personnes Handicapées
PNDS	Protocoles Nationaux de Diagnostic et de Soins
SNDS	Système National des Données de Santé

CONTENT

1. GENERAL INFORMATION.....	8

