5.4 Recruitment methods and feasibility

A random sample of patients will be drawn upon receipt of the CO BNDMR file by the URC ECO. The URC ECO will contact the sampled centers to inform them of the study project, the number of eligible patients in their center and their study ID, and will provide them with the associated documents (protocol, information letter to be given to the patient). Follow-up centers will be able to return to CO BNDMR to obtain the BaMaRa ID of sampled patients, in order to retrieve their contact in the application. Once they have been properly identified by the center, patients and/or their primary caregivers will be contacted by the CRA of their follow-up center, via an information letter explaining the purpose and modalities of the study. The questionnaire will be sent to them in the same letter, so that they can familiarize themselves with it and to give them time to gather the necessary information (expenses, etc.). The main caregiver will then be identified during the call following this letter.

With the BNDMR reporting a preliminary enrolment of around 2,028 DMD patients as of March 1, 2022 [9], the feasibility of the number of subjects required for this study will be ensured.

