6 GENERALE ORGANISATION

6.1 Study calendar

[figure not shown]
Inclusion period: 6 months (01/2024 - 06/2024)

Duration of participation for each patient/caregiver: completion of questionnaire (60 minutes max)

Total study duration: 6 months (01/2024 - 06/2024)

Anticipated start of inclusion: 01/2024

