8.3 Statistical methods

Cost data will be described in terms of means, variances, and confidence intervals. The normality or non-normality of the cost distributions will be checked. Costs (direct and indirect) will be described among patients living as of December 31, 2023. Analyses will also be conducted by level of mobility.

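### The BNDMR sampling frame closes on 1 January 2023 but section 6.1 sets inclusions for January to June 2024, so some patients who meet section 5.1 cannot be drawn

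*Combined protocol and SAP*

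**What the plan says.** Five places bear on who can be sampled and when.

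- **Frame (5.3).** "The patient identification period runs from the start date of inclusions in the BNDMR (2017) to January 1, 2023".
- **Draw (5.4).** "A random sample of patients will be drawn upon receipt of the CO BNDMR file by the URC ECO". No second extraction is described. Section 8.4 replaces non-respondents with new pairs but names no other source for them.
- **Eligibility (5.1).** "Patients of any age with DMD diagnosed more than 6 months ago", with no calendar limit, and patients "who are alive at the time they are asked to participate in the study".
- **Calendar.** Section 6.1 gives "Inclusion period: 6 months (01/2024 - 06/2024" and "Anticipated start of inclusion: 01/2024". The synopsis, under study duration, still gives "Inclusion period: 6 months (01/2023 - 06/2023".
- **Analysis (8.3).** "Costs (direct and indirect) will be described among patients living as of December 31, 2023". Section 8.2 takes everyone surveyed as the analysis population.

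Section 8.1 states the aim of a sample representative of the BNDMR population.

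**The concern.** The date in 5.3 determines which patients are in the file from which the sample is drawn. If it is followed as written and interviews take place in 2024, the effective rule is registration by 1 January 2023. That is stricter than the 6-month rule in 5.1.

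The patients lost are defined by recent diagnosis or recent registration. Replacement pairs taken from the same file cannot restore them. The loss does not shrink as interviews accumulate, and none of the analyses in section 8 would reveal it. Cost by severity stage is a secondary criterion (4.2.2), and section 2.1 links the project to a gene therapy being tested in young children. Thin coverage of recently diagnosed patients therefore touches a part of the results that the study is meant to supply.

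**Working it through.** **1. The plan's own figure.** Section 8.1 uses a coefficient of variation of 1 and a relative precision of 15%. The confidence level is not stated; I assume 95% two-sided.

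n = (1.96 × 1 / 0.15)² = 170.7, rounded up to 171. This agrees with the plan and does not depend on the frame date.

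**2. Length of the gap.** Gap = (contact date minus 6 months) minus 1 January 2023, set to zero if negative.

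| Calendar | Contact date | Latest eligible diagnosis (approx.) | Gap |
|---|---|---|---|
| 6.1 | 1 January 2024 | 1 July 2023 | about 6 months |
| 6.1 | 30 June 2024 | 30 December 2023 | about 12 months |
| Synopsis | 1 January 2023 | 1 July 2022 | 0 |
| Synopsis | 30 June 2023 | 30 December 2022 | 0 |

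Patients diagnosed before 2023 but first registered after the cut-off are also outside the frame. The documents give nothing from which to count them, so they are not in the figures below.

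**3. Number missed.** The documents give no rate of new registration. Section 2.1 gives 150 to 200 affected newborns a year, which I use as the upper part of the range. I add 75 a year as a low assumption, for the reason given under the objection. Missed = rate × gap in years. Share = missed / (2,028 + missed), where 2,028 is the gross count at 1 March 2022 (2.3), used as a stand-in for the frame.

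| Assumed rate per year | Missed at start (6 months) | Missed at end (12 months) |
|---|---|---|
| 75 | 38 (1.8%) | 75 (3.6%) |
| 150 | 75 (3.6%) | 150 (6.9%) |
| 200 | 100 (4.7%) | 200 (9.0%) |

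In expectation this is 0.018 × 171 = 3 to 0.090 × 171 = 15 of the 171 pairs.

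**4. Effect on the mean.** Let f be the share missed and r the cost of missed patients relative to the frame average. Overstatement = 1 / ((1 − f) + f × r) − 1.

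For illustration, suppose that all missed patients are ambulatory and use the Portuguese non-medical costs in Table 1: EUR 11,890 ambulatory and EUR 29,717 non-ambulatory. The ambulatory share of the frame is not given; I take 30 to 70%.

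| Ambulatory share | Frame average (EUR) | r | Overstatement, f = 1.8% | Overstatement, f = 9.0% |
|---|---|---|---|---|
| 30% | 0.3 × 11,890 + 0.7 × 29,717 = 24,369 | 0.488 | 0.9% | 4.8% |
| 50% | 20,804 | 0.572 | 0.8% | 4.0% |
| 70% | 17,238 | 0.690 | 0.6% | 2.9% |

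The range is roughly 0.5 to 5%.

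**5. The survival date in 8.3.** With 2024 inclusions, anyone alive when asked was alive on 31 December 2023, so the restriction removes nobody. With 2023 inclusions it would remove participants who die between interview and year end, against 8.2. On that calendar the gap in step 2 is zero, so the two problems do not occur together.

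**The case against.** **It may be only a date that was not updated.** This is the likeliest origin. The cut-off fits the synopsis calendar exactly, and the synopsis version date (15/11/2022) precedes that of the protocol (12/01/2023). The gap exists only if 6.1 stands and 5.3 is left alone. But 5.3 is the instruction for building the file, so following the current text produces the loss.

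**The birth figures probably overstate registrations.** Section 2.1 says that over 90% of children reach adulthood. Eighteen birth years × 150 × 0.9 = 2,430 minors, already above the 2,028 patients of all ages in the registry. Delay to diagnosis explains part of this, but registration probably runs below the birth rate. This stands, and it is why the range starts at 75. The 9.0% also applies only to contact at the very end of June 2024.

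**The one-year retrospective horizon (7.2) might justify leaving out recent diagnoses.** At a contact on 1 January 2024, everyone in the gap is 6 to 12 months from diagnosis and lacks a full year. The protocol does not give this reason, 5.1 admits such patients, and several recurring items in 7.3 are collected over a representative or last month. By 30 June 2024 the cut-off also removes patients diagnosed 12 to 18 months earlier, who do have a full year.

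**Stronger readings that the documents do not support.**

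- A reader might put the overstatement near 6% by entering the ambulatory to non-ambulatory ratio (11,890 / 29,717 = 0.40) as r, which at f = 9.0% gives 5.7%. That ratio equals r only if the frame holds no ambulatory patients.
- A reader might infer that the age range of the gene therapy trials is missing. Children aged 2 to 7 diagnosed and registered before the cut-off remain in the frame.
- A reader might take it as established that the missed patients are young and ambulatory. The documents give no age at diagnosis. The inference fits section 2.1, where walking is lost on average in early adolescence, but it remains an inference.

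**Conclusion.** The point holds as a frame coverage error under the section 6.1 calendar. Eligible patients diagnosed from 1 January 2023 until 6 months before contact, and those first registered after the cut-off, have no chance of selection. This runs against the representativeness aim in 8.1.

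The size is modest. The count rests on the assumed registration rate and on using 2,028 as the frame. The bias rests further on missed patients being ambulatory and on Portuguese costs. Even at the top of its range, the overstatement of the mean is well inside the 15% precision target. The effect falls mainly on recently diagnosed and early-stage patients; how much it distorts any one age stratum cannot be computed, because the four age groups are not defined.

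The wording of 8.3 adds no weight to this point. It is a consistency matter only.

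**What to change.** 1. In 5.3, replace the fixed end date with wording such as: *to the date of the BNDMR extraction used to draw the sample, shortly before the first mailing; a diagnosis more than 6 months old is checked at contact.*
2. Align the synopsis calendar with 6.1.
3. As a consistency edit, replace the 31 December 2023 survival condition in 8.3 with wording that matches 5.1 and 8.2: alive when asked to participate, and all participants surveyed analysed.

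The cost is a change of wording and a later extraction date for a file that has to be produced anyway. No extra pairs are needed and N stays at 171. The change has to be made before the sample is drawn.

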5.4 Recruitment methods and feasibility

A random sample of patients will be drawn upon receipt of the CO BNDMR file by the URC ECO. The URC ECO will contact the sampled centers to inform them of the study project, the number of eligible patients in their center and their study ID, and will provide them with the associated documents (protocol, information letter to be given to the patient). Follow-up centers will be able to return to CO BNDMR to obtain the BaMaRa ID of sampled patients, in order to retrieve their contact in the application. Once they have been properly identified by the center, patients and/or their primary caregivers will be contacted by the CRA of their follow-up center, via an information letter explaining the purpose and modalities of the study. The questionnaire will be sent to them in the same letter, so that they can familiarize themselves with it and to give them time to gather the necessary information (expenses, etc.). The main caregiver will then be identified during the call following this letter.

With the BNDMR reporting a preliminary enrolment of around 2,028 DMD patients as of March 1, 2022 [9], the feasibility of the number of subjects required for this study will be ensured.

6 GENERALE ORGANISATION

6.1 Study calendar

[figure not shown]
Inclusion period: 6 months (01/2024 - 06/2024)

Duration of participation for each patient/caregiver: completion of questionnaire (60 minutes max)

Total study duration: 6 months (01/2024 - 06/2024)

Anticipated start of inclusion: 01/2024

6.2 Schematic diagram

6.3 Conduct of the study

6.3.1 Inclusion

Patients likely to participate in the study will be identified following the sampling procedure. Each patient/caregiver pair will first be contacted and informed by letter of the existence of the survey. Any explanations required for a proper understanding of the study will be given to the patient and/or his or her main carer in an information letter explaining the objectives and progress of the protocol.

If the patient and his/her primary caregiver do not object to their participation in the study within 30 days of receiving the information letter, they will be considered as included in the study.

6.3.2 Questionnaire answering

The questions are taken from published questionnaires, and a validation of the questionnaire's comprehensibility and acceptability will be carried out on at least 2 child/caregiver and 2 adult/caregiver patients before the information letters are sent out [10].

The standardized questionnaire (see appendix) will be sent to patient/caregiver pairs with the information letter. This will enable participants to gather the information they need to answer the questionnaire.

A clinical research associate from the center which usually cares for the DMD patient or, failing that, from the URC Eco, will then contact the patient and/or his/her main carer by telephone. The interview, lasting a maximum of half an hour, will be based on the questionnaire and will ensure that the participant has understood the questions and that all the required data have been collected.

Variables intended to ensure representativeness or to enable sample adjustment will be collected at inclusion, including commune of residence (used only for adjustment), as well as:

- Patient characteristics: gender, month and year of birth, ambulatory or non-ambulatory status;
- Characteristics of the main caregiver: age, sex, relationship to the patient (degree of kinship, partner or other non-family relationship), family structure (couple, characteristics of other children, etc.).

Variables for cost analysis will also be collected (see chapter 7 + appended questionnaire).

6.4 Temporary or permanent shutdown rules

Subjects may object to their participation and ask to leave the study during the interview, for whatever reason. In the event of premature exit (questionnaire not fully completed), and if the subject does not object, the data collected up to the point of objection will be analyzed.

7 COST EVALUATION

7.1 Perspective

The societal perspective (integrating amounts financed beyond the perspective of compulsory health insurance, i.e. patient out-of-pocket expenses, non-reimbursed costs and lost productivity) will be retained.

7.2 Timeframe

The time horizon will be one year (retrospective) of patient care.

7.3 Identification et quantification des ressources consommées

The resources consumed will be identified and quantified:

1. Non-reimbursable health resources

- Name and weekly quantity of OTC drugs consumed in a representative month;
- Name, type and quantity of other OTC products (e.g. small medical devices, oral nutritional supplements, etc.) purchased in a representative month;
- Number and type of paramedical consultations carried out in a representative month;
- Number and type of non-reimbursable technical equipment for disability compensation purchased since DMD diagnosis.

2. Ressources de la sphère médico-sociale

Medico-social costs include those incurred by the medico-social sector. This includes social and medico-social establishments and services (ESMS) and social action assistance.

There are two main types of establishment:

- Establishments and services for disabled adults;
- Establishments and services for disabled children and adolescents.

The following variables will be collected:

- Frequency, duration and type of stay in a social and medico-social institution in the last month;
- Number of visits to a medical-social service in the last month.

3. Support for schooling and Professional life

- Schooling programs;
- Socio-professional support services.

The following variables will be collected:

- Number and type of support staff (carers, special educators, social workers, etc.) in the last month;
- Type of schooling, specific assistance and how many hours, if not in which structure, and what additional costs in the last month;
- Working hours, support arrangements and how many hours over the past month.

4. Other non-medical resources

- Recours à une aide hors secteur sanitaire pour les actes de la vie quotidienne (ménagère, auxiliaire de vie, etc.), type et nombre d'heures hebdomadaires ;
- Aménagements réalisés au domicile, depuis le diagnostic ;
- Adaptation du(des) véhicule(s) et/ou acquisition d'un véhicule aménagé, depuis le diagnostic
- Modalité des transports non médicaux, fréquence et kilométrage hebdomadaire.

5. Informal help

- Number of caregivers over 18 years old in total, degree of kinship;
- Number of hours spent with the patient providing support for care, daily living activities, and instrumental activities of daily living.

6. Productivity loss

- For the primary caregiver: Changes in situation, absenteeism, and presenteeism related to DMD;
- For the patient: Absenteeism and presenteeism (school or work) related to DMD.

7. Help and allocations

The allowances include disability compensation (PCH), compensatory allowance for a third party (ACTP), child disability education allowance (AEEH) and its supplements, adult disability allowance (AAH), and the increase for independent living (MVA).

The following variables will be collected:

- Allowances received, type, and total amount;
- Destination (compensation for non-medical costs, loss of productivity, etc.): not requested in the questionnaire; this item will be subject to a post hoc analysis

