7.4 Resource valorization

Direct medical and non-medical costs will be annualized, assuming consistent/representative resource use over the measurement period (months).

1. Non-reimbursable healthcare resources

- Weekly quantity valued at the average sale price;
- Quantity of other over-the-counter products (e.g., medical devices, oral nutritional supplements (ONS), etc.) valued at the average sale price;
- Number of hours of paramedical care valued at the corresponding wage/convention rate (if available);
- Quantity of technical equipment for disability compensation valued at the average sale price.

2. Medico-social resources

- Use of medico-social support: number of hours valued at the service rate, or, if unavailable, at the average hourly wage of equivalent professionals in France;
- Total costs of stays and consultations in medico-social facilities related to the specified medical condition within the medico-social sector.

3. Other non-medical resources

- Home adaptations: family expenses (lifetime);
- Modification of vehicles and/or purchase of an adapted vehicle: family expenses (lifetime);
- Non-medical transportation: weekly mileage valued according to the mileage reimbursement rate for personal vehicles.

4. Informal help

Care hours provided by caregivers valued at the cost of a replacement salary, according to the Proxy Good Method (PGM), and hours for activities of daily living valued at the average salary of a housekeeper.

5. Productivity loss

Lost work hours related to the DMD (Degenerative Motor Disorder) that do not pertain to caregiving, valued at the average hourly wage in France.

6. Assistance and allocations

Total monthly benefits related to DMD (Degenerative Motor Disorder) received by the patient and/or the family in the medico-social sphere.

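### School support is counted over one month in January–June interviews and annualized as constant use, which overstates its yearly cost

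*Combined protocol and SAP*

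**What the plan says.** Section 7.3 item 3 collects school support as "Type of schooling, specific assistance and how many hours, if not in which structure, and what additional costs in the last month", and the related staff as "Number and type of support staff (carers, special educators, social workers, etc.) in the last month". Item 2 uses the same window for medico-social stays, "Frequency, duration and type of stay in a social and medico-social institution in the last month", and for visits, "Number of visits to a medical-social service in the last month". Item 1 is worded differently; for over-the-counter drugs, for example, it asks for "Name and weekly quantity of OTC drugs consumed in a representative month".

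The calendar in section 6.1 gives "Inclusion period: 6 months (01/2024 - 06/2024", with a total study duration over the same six months. The abstract has the same months in 2023. Section 9.1 says that the interview is the act of inclusion, so the inclusion period is the interview period.

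The target is annual. Section 7.2 states: "The time horizon will be one year (retrospective) of patient care". Sections 4.2.1 and 4.2.2 define the main and secondary criteria as mean annualized costs, in total and by type of cost. Table 2 lists school support among the medico-social direct costs. The annualization rule in section 7.4 is: "Direct medical and non-medical costs will be annualized, assuming consistent/representative resource use over the measurement period (months". The documents contain no school-week multiplier, question on holiday use or seasonal adjustment.

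**The concern.** A one-month count represents a year only if use is level, or if the recalled months are spread over the year as the use is. School support is unlikely to be level, since it depends on school being open. The planned recall windows also leave out the longest closure. The result is an error with a direction, upward, which more interviews would not reduce.

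What is at stake is chiefly the secondary criterion by type of cost, where school support sits in the medico-social group. The main total is affected less. The plan already has safer wording in item 1 (a representative month) but does not use it for the items most tied to a calendar. Even that wording would not settle the matter for school support, because a typical term month times 12 still counts the closed weeks.

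**Working it through.** **Inputs from the documents.** One-month recall (7.3 items 2 and 3); interviews January to June (6.1, 9.1); one-year horizon (7.2); constant-use annualization (7.4); coefficient of variation 1, precision 15%, 171 pairs (8.1).

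**Assumptions, not in the documents.** School support is nil when school is closed, including a summer closure; 36 to 40 school weeks a year; school items are 2 to 10% of the reported total for school-age patients.

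**1. The plan's own figure.** With a two-sided 95% level (assumed, as none is stated), n = (1.96 × 1 / 0.15)² = 170.7, rounded up to 171, which reproduces section 8.1. The half-width at 171 is 1.96/√171 = 15.0%. This covers sampling error only. A calendar bias is not part of it, and the sample size does not change.

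**2. The window.** Interviews from January to June with a one-month look-back cover about December to June. July to November, and so the whole summer closure, is in no recall window.

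**3. Upper bound for school items.** If every family reports a full term month, annualized/true = 52 / school weeks:
- 40 weeks: 52/40 = 1.30
- 36 weeks: 52/36 = 1.44

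**4. Some short breaks inside the window.** Let the window be W = 6.5 months, the summer closure c months, other closures o months a year, and i the share of those other closures that falls inside the window. Then

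annualized/true = [(W − o·i)/W] ÷ [(12 − c − o)/12].

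The grid was c = 1.5 or 2, o = 0 to 2, and i = 0.5 to 1:
- highest (c = 2, o = 2, i = 0.5): (5.5/6.5)/(8/12) = 1.27
- low (c = 1.5, o = 1.5, i = 1): (5/6.5)/(9/12) = 1.03
- extreme (c = 1.5, o = 2, i = 1): (4.5/6.5)/(8.5/12) = 0.98

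The overstatement is thus roughly 3 to 27%. It vanishes only in the extreme case, where every short break of the year falls inside the window. The 1.27 corresponds to 52 × 8/12 = 34.7 school weeks, slightly below the 36 to 40 assumed in step 3. A direct example in weeks: 16 weeks closed, 9 of them in summer, and 5 of the other 7 inside a 30-week window gives (25/30)/(36/52) = 1.20.

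**5. Effect on the total, school-age patients.** Excess as a share of the reported total = school share × (1 − true/annualized).
- Upper-bound ratios: 2% × (1 − 40/52) = 0.5%; 10% × (1 − 36/52) = 3.1%
- Ratio 1.20: 2% × (1 − 1/1.20) = 0.3%; 10% × (1 − 1/1.20) = 1.7%

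**6. Medico-social stays.** If a share s of yearly use falls in July and August and the rest is even over the other 10 months, annualized/true = 12 × (1 − s)/10 = 1.2 × (1 − s). This is 1.20 at s = 0, 1.00 at s = 1/6, 0.84 at s = 0.30 and 0.60 at s = 0.50.

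**The case against.** **The factor of 12 is not written.** This is true. Section 7.4 gives no multiplier, and its sentence names direct medical and non-medical costs, while Table 2 puts school support in a separate medico-social group. But a one-month count that feeds an annualized criterion under constant use implies 12. If the sentence does not reach school support, that item has no annualization rule at all. The text must be completed either way.

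**The analysis plan can settle it later.** Section 8.5 promises a detailed plan before the database is frozen, and a school-week multiplier could be set there. That helps only if the data allow it. Hours recalled for a month that was partly a break cannot be turned into hours per school week without knowing how much of the month was term.

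**The window may not be so strict.** Section 8.1 lets interviews continue until 171 is reached, and section 6.3.1 treats families as included after 30 days without objection, which could precede the call. Some interviews might therefore run into summer. The stated study duration still ends in June, so the point is about the plan as scheduled.

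**The questionnaire is not in the text reviewed.** It may ask something different. Section 7.3 as written does not.

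**30 to 44% is a ceiling.** A reader might take it as the expected error. It requires every reported month to be full term, whereas a December-to-June window is likely to include short breaks. This objection stands, and the lower range in step 4 is the fairer description.

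**Stays need not be biased.** This also stands. Nothing in the documents shows that stays are seasonal, and continuous residence is annualized correctly from one month.

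**Conclusion.** As scheduled, the recall windows miss the summer closure, and the constant-use rule overstates the annual cost of school support. The direction rests on two assumptions: support stops when school closes in summer, and the short breaks are not nearly all inside the window. The size is at most 30 to 44% of the school item with 36 to 40 school weeks, and roughly 3 to 27% once short breaks are allowed for. With an assumed 2 to 10% share, the total for school-age patients is overstated by at most about 0.5 to 3%, and by less averaged over all ages. This is modest for the main criterion but material for the cost-by-type result, and cheap to correct.

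Three stronger readings are not supported:
- **Stays are misstated in a known direction.** They are not: the bias is nil if one sixth of yearly use falls in July and August, and can go either way otherwise.
- **Age-group comparisons are distorted.** None is planned. The study is non-comparative (4.1), age is a sampling stratum (8.1), and the subgroup analysis is by mobility (8.3).
- **One-month counts undermine the planning coefficient of variation of 1.** Section 8.1 takes that value from other countries' data, and the documents give nothing from which to size such an effect.

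**What to change.** - **Section 7.3 item 3:** record school support as hours per school week.
- **Section 7.4:** state that these hours are multiplied by the number of school weeks in the reference year, and name that number and its source. Keep constant-use annualization for items that do not follow the school calendar, and say explicitly that the rule covers the medico-social group.
- **Optional, section 7.3 item 2:** consider adding a question on medico-social stays over the past 12 months, which matches the horizon in section 7.2.

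The main change costs one reworded questionnaire item before mailing and one added line in section 7.4; the sample size is unaffected. The optional question trades possible seasonal error for longer recall, so it is a matter of judgement and the main point does not depend on it.
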